8.1.18 Cognition

The Blessed Orientation-Memory-Concentration (BOMC) test consists of six questions designed to screen for cognitive impairment. A score >11 signifies cognitive impairment. The test-retest reliability is high (Spearman rank correlation $_$ 0.96; P $_$ 0.001) [104]. The BOMC has excellent validity as a screening instrument, correlates highly with clinicians' ratings of dementia severity (r $_$ 0.89), predicts results from a longer (26-item) mental status questionnaire, and discriminates between patients with mild, moderate, and severe cognitive deficits [105].

The BOMC has been implemented in the geriatric assessment for older cancer patients in Cooperative Group Clinical Cancer Trials (CALGB).[64] The BOMC has also been recommended by the International Society of Geriatric Oncology for evaluation of cognition in older cancer patients.[106]

Assessment for cognition during study follow up will be allowed within a period of 3 months before or after the corresponding assessment time point in Table 1.

Cognition will be assessed **only in patients 60 years and older** at:

Protocol 2368.00

- 1) Study enrollment.
- 2) At 6 and 18 months after day 0 of allogeneic HCT for recipients of HTC or at 12 and 24 months from study enrollment for patient not treated with HCT.

8.1.19 Questions about some geriatric problems only for patients 60 years and older

The questionnaire will ask the following questions:

- 8.1.19.1 Vision
- 8.1.19.2 Hearing
- 8.1.19.3 Other physical problems or illness
- 8.1.19.4 Falls

These variables will be assessed once at:

- 1) Study enrollment

8.1.20 Recovery Survey:

The recovery survey will ask the following questions:

- 8.1.20.1 Marital status
 - 8.1.20.1.1 Change since diagnosis of AML
 - 8.1.20.1.2 Current marital status.
- 8.1.20.2 Work status
 - 8.1.20.2.1 Change since diagnosis of AML
 - 8.1.20.2.2 Current work status.
- 8.1.20.3 Family income
 - 8.1.20.3.1 Change since diagnosis of AML
 - 8.1.20.3.2 Current income.

These variables will be assessed once at:

- 1) 24 months from study enrollment.

Protocol 2368.00

Table 1: Timing of Study Evaluations*

	Timing of assessments							
		Months						
Measures	Enrollment	1	3	6 ∇	9 ∇	12 ∇	18 ∇	24 ∇
	£							
Patient-reported socio-demographic & health behaviors survey	X							
AML diagnostic features	X							
HCT-CI, comorbidities, and laboratory tests	X		X	X				X
KPS	X		X	X	X	X	X	X
Physician preference surveys	X	X	X	X**				
Patient Preference Survey	X	X	X	X**				
Availability of donor, and its type	X	X		X				
Treatment details		X	X	X	X	X	X	X
AML response evaluations		X	X	X	X	X	X	X
Toxicity grading		X	X	X	X			X

Protocol 2368.00

QOL measures in Questionnaire Packet	X	X	X	X	X	X	X	X
Function measures (Walk Test)	X	X	X	X	X	X	X	X
Timed Up-Go test for FI calculation	X			X				X
Cognition in older patients	X					X		X
Geriatric problems in older patients	X							
Outcomes data		X	X	X	X	X	X	X
PFT, Blood Tests, Urine test (FH site only)	X							
Patient-reported Recovery survey								X

*All dates of assessments are recommended dates that could be adjusted (within a limit of 30 days) to take into account suitability of patients' clinical status and reasonable recovery of peripheral blood counts.

[figure not shown]
[figure not shown]
**Assessment will be done if the patient has not undergone HCT

£Assessment should be done after enrollment and preferably before the start of treatment. However, a grace period of one week after the start of treatment is allowed to consent the patient and introduce the assessments. Surveys should be completed by the patients based on their experiences before start of treatment and they should be returned as soon as possible after being completed.

¥If a patient received an allogeneic HCT, then study assessments will be adjusted to reflect the durations of pre-transplant and 3, 6, 12, and 18 months after day 0 of HCT.

Protocol 2368.00

Figure 3: Prospective observational study schema

Protocol 2368.00

9.0 STUDY PROCESS

Case Report forms (CRF): CRFs will be collected by the study coordinator at FHCRC and at outside centers. The components of the CRFs should reflect the previously described study evaluations (Table 1).

The CRF will guide the collection of non-patient-reported data into an electronic database through the program REDCap (Research Electronic Data Capture). Though it's not possible to translate a paper CRF directly to an electronic format due to the inherent differences between the two mediums, the translation from paper to computer will stay true to the original format as much as possible. The REDCap platform has an extensive logging feature in order to accommodate audit trails. Every design change, record addition or edit, and data export is automatically logged by user with a date-time stamp. This log is searchable by users with the appropriate user rights through the standard REDCap web-interface. The entire log for a project is exportable to a CSV file at any time by users with the appropriate user rights. REDCap also supports the optional "Data Resolution Workflow" feature, which enables users to open up issues for each variable and each record individually. They can then assign the issue to the appropriate user for resolution. Finally, users have the ability to run a host of standard data quality queries (like missing values, outliers, etc.) in order to check the integrity of the data. Users can also tailor custom data quality queries to check specific criteria relevant for that project. These queries can be run in the same way as the standard data quality queries or in real time at the time of a form submittal by a user.

Data from source documents will be used to transcribe critical protocol data on CRFs. Source documents are documents where patient data are recorded and documented. They include, but are not limited to, clinical summaries, laboratory results, pharmacy dispensing records, and pathology reports. The outside sites will send copies of appropriate source documents to the Coordinating Center (FHCRC) for performance of quality assurance evaluations of the entered data. The original documents will be kept in secured buildings at FHCRC. For each patient, the outside sites will also send a hard copy of the first page of the CRF, which includes the PI's signature verifying each patient's eligibility.

PFT and Biomarker Sample: At enrollment, participants enrolled at FHCRC or Seattle Cancer Care Alliance Southeast Lake Union (SCCA-SELU) will be assessed for DLco and FEV1. If the patient has already been assessed for these tests as part of his/her medical care, this data will be collected from the patient's records. The patient will also be asked to provide a blood sample, either at SCCA-SELU if seen as an outpatient or at UWMC if seen as inpatient, prior to start of initial therapy. Samples will be routed to Research Testing Service (RTS) at UWMC. The patient will also be asked to provide a urine sample to check the albumin-creatinine ratio, as well as urine analysis.

Completion of Surveys: At enrollment, the patient surveys will be administered by the data coordinator in Seattle and collaborating centers' staff at the other sites. Questions raised by patients about the surveys will be answered by the administering staff. Contact information of the Seattle data coordinator will be available for patients enrolled at the outside centers to answer any additional questions about the study or the surveys. All follow-up patient surveys will be collected by the data coordinator located in Seattle. For each completed survey, the patient will receive \$20 in remuneration, for a total maximum of \$160 over two years.

Collecting/sending surveys: The patient will be asked ahead of time about his/her preferred method of completing the survey: email or pencil-paper (See study document "Method of Communication"). The web-based questionnaire is preferred but the pencil-paper method will be available per patient preference. The method used for collection of surveys will be recorded for each patient. Through the website, the coordinator

Protocol 2368.00

will email the survey at the proposed surveying times and the participant can then fill the survey packet electronically.

Patients who have initially requested the paper-pencil questionnaire will have the questionnaire mailed to their home address with prepaid return-envelopes. Once a completed survey is received, the study coordinator will enter data from the surveys into REDCap. The coordinator will periodically update the survival/death data to ensure the patient is alive prior to initiating the survey reminders.

The study coordinator will contact the patient weekly after sending the survey to encourage completion. At each weekly call (up to one month after sending the survey), the patient will be offered the option to fill out the survey over the phone by answering questions from the study coordinator. The study coordinator will then enter the answers into REDCap. Reasons for inability to complete a survey packet will be collected and recorded. Study staff will carefully review all self-completed paper forms for ambiguous responses and missing data, and clarify these with the participant. The method of survey collection will be recorded.

Physician consent and assessments will be sent to FHCRC physicians either through REDCap, via email, or inter-departmental mail. The same methods will be used by study coordinators at outside centers to collect answers from their respective physicians. Follow up assessments will be handled by FHCRC study coordinators for all physicians, preferably using REDCap communications.

Data Security

Any publication or presentation will summarize patient data and not refer to patients by unique patient number or name to assure patient confidentiality. The licensed medical records department, affiliated with the institution where the patient receives medical care, maintains all original inpatient and outpatient chart documents. Patient research files are maintained by a designated research coordinator at each institution and kept in a locked room with access restricted to personnel. A study specific database will also use the unique patient number and will not include patient names. Access to the database will be restricted by electronic password protection and restricted access to computers (i.e., locked offices).

REDCap is located on two servers that are protected by a firewall. Each individual that needs to access REDCap (that is, the study coordinators and investigators) has his/her own account. REDCap implements authentication to validate the identity of end-users that log in to the system. Each account can only have access to projects in REDCap that the person has been invited to. The FHCRC Study Coordinator will determine which part of the project other users have access to. REDCap utilizes an auto-logout setting, which is customizable (default auto-logout time is 30 minutes), and will automatically log a user out of the system if he/she has not had any activity (e.g. clicking, typing, moving the mouse) on his/her current web page for the set amount of time. This prevents someone else from accessing the account and project data if a workstation is left without properly logging out or closing the browser window. To help protect and secure the data stored in REDCap's back-end database, the software application employs various methods to protect against malicious users who may attempt to identify and exploit.

Study Participant Committee:

A number of 12 study participants will be invited to join the study stakeholders. Two participant-stakeholders will be selected randomly from each site and will be involved in research discussions. We will use a random number generator (found at www.randomnumbergenerator.com) to select two numbers between 1 and 100 which will coincide with participants' unique study-related ID. We will generate new numbers for each site. These two participants will be contacted via telephone and will be provided with an explanation about the study objectives and role of stakeholders. If the participant declines participation as a stakeholder, we will use the website to select a new number until we have two participant-stakeholders from each site. Our goal is to

Protocol 2368.00

represent all five sites, both genders, various age intervals above 60 years old, and variable burdens of comorbidities.

The construction of this committee preferably to be completed within the first year of the study enrollment.

The study participant committee members will be asked to evaluate our methods in translating key results into language that can be communicated to other participations, in order to improve participation and minimize losses to follow-up, and to future patients, to ensure broad dissemination of results.

Completion of Expert Opinion Surveys:

Upon submission of the completed survey, participating physicians will be entered in a drawing to win one of twenty \$50.00 Amazon gift cards. Winners will be randomly selected and notified by email.

10.0 ADVERSE EVENTS

Since the proposed studies are not treatment protocols, there will be no risks in addition to those explained to the patients as parts of their treatments for AML.

There is a risk of breach of confidentiality. We have taken all possible measures to avoid this risk. We will explain to patients this risk in the consent form and we will assure them about our methods to protect their confidentiality.

Psychological and social stress might be associated with informing the patients of their comorbidity scores and how these might impact their treatment outcomes. Each patient has a specified family member, guardian, or friend (depending on the age of patient) who provides support for patients during and after the survey. Potential psychological stress includes knowledge of transplant related complications and fear of treatment failure, chronic illness, and potential death. Each treatment center has trained psychologists, psychiatrists, and social workers available for patients and their families.

PFT could carry the risk of the patients developing cough or feeling light-headed or dizzy. It can also cause a feeling of pressure in the chest, belly, or head. These tests are done in clinical facilities and physicians are available to deal with any situation resulting from these tests.

There is a rare risk of bleeding during collection of research samples. It is rare because we will collect these samples only at baseline before the patient has received any chemotherapy that might result in lowering their platelet counts.

Per IRB rules, only related, unexpected, and serious adverse events will be reported to the appropriate IRB, within ten (10) calendar days of becoming aware of the event.

10.1 Reporting Serious and Unexpected Adverse Events (SAE) from Participating Sites

All unanticipated serious adverse events that are considered related to study participation must be reported to the FHCRC Investigator within 72 hours of learning of the event. The immediate telephone report must be followed by a report faxed to the FHCRC Study Coordinator at [contact]. Any follow-up information must be submitted as soon as the relevant information is available.

Protocol 2368.00

11.0 STATISTICAL CONSIDERATIONS

11.1 Introduction and sample size

To improve the strength of the findings as well as reporting of these findings, we will follow the recommendations of STROBE Statement (see study document ‘STROBE Criteria’) which provides guidelines of how to discuss and report study design, analysis, and findings in manuscript writing.

There is no targeted number for enrollment on this study. Instead, we plan to enroll all eligible patients continuously for duration of 36-40 months from study activation. We anticipate enrolling approximately 1000 patients from all sites but we will allow enrollment of more patients if enrollment rates were unexpectedly higher.

Based on a preliminary screen of the SCCA records over years 2008-2009, approximately 180, 125, 120, and 75 eligible patients with AML were seen annually at the 4 collaborating institutions, respectively, for an annual total of 500 patients. We anticipate enrollment rate of approximately ~65% resulting in a total of approximately 1000 patients observed over 3 years. Based on a preliminary screen, we anticipate that 50% (n=500) will be ≥60 years of age. Among the remaining 500 younger patients, we would anticipate (based on historical distribution of comorbidity scores among HCT recipients) that approximately 35% (n = 170) will have significant comorbidities (scores of ≥3). This suggests that the combined cohort of older or medically infirm patients eligible for studying the rate of receiving allogeneic HCT will be approximately 670 patients over 3 years. **Table 2** shows an estimate of the minimal increment in incidence of HCT detectable with 80% power at the 2-sided 0.05 level of significance, for varying assumptions about the prevalence of the risk factor. These estimates assume a time-to-event analysis, 25% overall incidence at 2 years post-initial therapy and 25% incidence of death without HCT as a competing risk.

Prevalence of risk factor or group	Increment in HCT incidence (HR)
10%	0.17 (1.9)
20%	0.13 (1.7)
30%	0.11 (1.6)
40%	0.10 (1.6)

For the comparison study, power calculations are complicated by the time-dependent nature of the treatment groups, as well as by likely non-proportionality in the hazard ratio for HCT. Were these factors not present, the expected 170 patients undergoing HCT compared to 505 who do not undergo HCT, would provide at least 80% power to detect an increase in OS of 13%, at the 2-sided 0.05 level of significance. Because of the large number of unknown assumptions it is nearly impossible to estimate the true power for the actual analysis that will be done, other than that the detectable effect size is likely considerably larger than 13%. Nevertheless, based on previous experience with time-dependent analyses (such as of chronic graft-versus-host disease after HCT),[107] the overall sample size should be sufficient to detect effects of meaningful clinical magnitude.

11.2 The probability and predictive factors for undergoing allogeneic HCT

(1) Based on sample size calculations (see **Sample Size section**), we anticipate total sample of 1000 patients contributing to this analysis. Patients of ≥60 years will be ~500 while those <60 years will be ~500 patients. Among younger patients: we anticipate 40% (n=170) will have high comorbidity scores. The cohort of combined older or medically infirm patients eligible for studying the rate of receiving allogeneic HCT will be approximately 670 patients.

(2) The rate of undergoing allogeneic HCT will be estimated for the whole observed population, comparing older/medically infirm patients to all other patients.

Protocol 2368.00

(3) Data from patients' preferred level of involvement in treatment decision-making will be analyzed by assessing the overall distribution of the most frequent answers among patients who received HCT versus conventional therapy, using chi-squared test. Comparisons of proportion of patients assigning a particular answer as most important will also be done using chi-squared test. The weighted Kappa-statistic will be used to assess the level of agreement or disagreement between the patient's and physician's responses. Marginal Cox model will be used to account for potential correlation between physician and patient preferences.[108]

(4) Differences in QOL scores between baseline and post-treatment assessments for each patient will be tested in an analysis of variance (ANOVA) model.[109]

(5) To identify independent predictive factors for the feasibility of allogeneic HCT, multivariate Cox proportional-hazards regression models will be used, treating HCT as the event of interest and death without HCT as a competing risk. Associations between the potential predictive variables, described under Methods, and the incidence of allogeneic HCT will be evaluated using a backward stepwise approach. Variables that are significantly associated with each outcome event ($P < .05$) will be included as covariate factors in the subsequent comparisons. Time-dependent covariates for multiple post-exposure therapies will be employed using previously described methods.[110] Results will be expressed as HR for each outcome.

11.3 Comparison of outcomes among older and medically infirm AML patients given allogeneic HCT versus conventional therapy

(1) Older and medically infirm patients who were prospectively enrolled for 2-years under SA2 and who completed initial intensive therapy will then represent a cohort of patients eligible to receive allogeneic HCT or additional conventional therapy ($n=670$). Based on preliminary screen of databases of collaborating centers, we estimate that approximately 25% of the 670 patients will undergo HCT within the time frame of the study. Patients who do or do not undergo HCT will be compared for NRM, OS, DFS, toxicities, QOL, function, utilization and satisfaction with care. Survivors at 3, 6, and 9 months will be compared for these two outcomes.

(2) Primary Outcomes: (i) Proportional hazards regression models for the sub-distributions of competing risks[111] will be used to evaluate impact of HCT and other factors on time-to-event outcomes (NRM, OS, and DFS). Since HCT may be received well after completion of induction and consolidation therapy, it will be analyzed as a time-dependent covariate,[110]so that the comparison is based on patients who have survived for comparable lengths of time. Similarly, patients who are not newly diagnosed at enrollment will be handled via left truncation – i.e., they will enter the set of patients at risk based on time since diagnosis. This analysis will be adjusted for the risk-stratification model, including comorbidities, disease response, age, and other variables; pre-exposure QOL scores; socio-demographic variables, including driving time to treating centers, income, marital status, and other variables; ranks of patient and physician surveys of decision-making style and treatment values; and the institution where the patient was treated. The evaluation of HCT as a risk factor may be complicated by the likely non-proportionality of hazards. In the short-term interval after HCT the risk of death may increase relative to those alive but not transplanted, then decline due to decreased relapse. We will assess this possibility by allowing the hazard ratio for HCT to vary by time after transplant in a time-dependent manner. All P values will be based on likelihood ratio statistics and will be 2-sided. Multivariate P values for a variable will reflect adjustment for all other variables in the model. Measures of precision for the HR or risk differences will be provided in form of confidence intervals.

(ii) Landmark analyses for all patients alive at 3, 6, and 9 months post-induction, based on prior history of HCT, will be used to partially compensate for the time-dependent nature of the intervention and early death. A possible approach to describe the effect of HCT on outcome will be to divide the time axis into short intervals (for example, 3-6 months) and to estimate the actual hazard of the event of interest during the interval in 3 different states: not transplanted, early after transplant, late after transplant. This will be based on a simple

Protocol 2368.00

exponential assumption: i.e., the number of events in each state divided by the number of person-years at risk in each state. These hazard rates would yield estimates of OS probabilities, which could then be combined to yield estimates of OS probability over longer intervals, for example 1 or 2 years. The usefulness of such estimates would depend on relative stability of the hazard rates as a function of time since initial therapy.

(iii) Given the expected bias in treatment selection and to further enhance our ability of obtaining accurate statistical inferences, we will use propensity scores. Propensity scores will estimate the probability on the basis of all patients and center characteristics that patients would proceed to allogeneic HCT with the use of proportional hazard model to adjust for between-group differences in the previously mentioned characteristics.[112] The magnitude of divergence of propensity scores between the two approaches will allow us to assess the amount of bias in treatment selection. Inverse-probability-weighting based on the propensity score will then be used as a secondary tool to adjust for differences between the two treatment-groups [113]. This approach will be implemented to create balance and it involves weighting each patient who received HCT by the inverse of the probability that he or she would be selected for HCT and weighting each patient who received conventional treatment by the inverse of the probability that he or she would be selected for conventional treatment. We will verify the performance of the propensity model by comparing the distribution of covariates and propensity scores between treatment groups both before and after inverse probability weighting.[114] Adjusted OS curves will be estimated using the inverse-probability-weighting approach of Cole and Hernan.[115] Assessment of benefit of either approach will be done in quintiles of propensity scores.

(iv) Sensitivity analyses will be performed to better understand any statistical disagreement between the models. First, OS curves for comparing both groups will be estimated using a double robust strategy of combining the inverse-probability weighting with the regression-based estimation [116]. Secondly, propensity scores will be used to construct matched samples from both groups to be used for simple matched pair analyses which adjust for confounding variables. Finally, we will use the method of Lin et al [117] to assess whether the observed differences in the rate of death could be due to an unmeasured confounder.

(3) Secondary Outcomes: **(i)** The relationship between the choice of treatment (HCT vs. non-HCT) and QOL, function, utilization, and satisfaction scores will be examined. Intra-patient differences will be used to analyze changes in QOL from baseline to follow-up assessments. Basic analyses will utilize paired t-tests (for changes over time) and two-sample t-tests (for comparison between groups). In order to make full use of the longitudinal data we will also use generalized estimating equations (GEEs) approach,[118] which can accommodate the within patient correlation structure and arbitrary patterns of missing data. Further, the GEEs approach would allow for the population-average interpretation which is an advantage over, for example, generalized linear mixed models approach.

(ii) The previously described statistical approaches will be used to adjust the comparisons between recipients of allogeneic HCT and conventional therapy for the pre-exposure measures of QOL and preference scores.

(iii) We will compare the quality-adjusted outcomes using the Q-TWiST methodology which weights survival time according to clinical status (alive without relapse or toxicity, relapse, and toxicity) [119-122]

(4) Tertiary Outcomes: **(i)** The risk factors for mortality after ICU admission in patients with AML will be examined. Survival analysis with logistic regression or Cox proportional hazards model will be used, depending on completeness of patient follow-up. Variables in the model will include the AML-comorbidity model score, history of HCT, AML disease status, absolute neutrophil count, use of life support devices, bacteremia, and creatinine. The above risk factors will be evaluated using AUC and c-statistic to inform development of a potential model to predict ICU mortality. **(ii)** The outcomes of patients with secondary AML will be evaluated as compared to patients with primary AML, after adjusting for percent blasts in the peripheral blood, white blood cell count, and performance status at time of presentation.

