The study procedures will be outlined and patients will have an opportunity to ask questions. If necessary, discussion about the study may take place by telephone. Signed informed consent is required for enrollment. If the patient is unable to provide written informed consent prior to questionnaire completion because of logistic limitations, questionnaires could be completed on the basis of verbal consent (See study document ‘Study Letters and Phone Script for Consenting). However, no research data will be entered into the database until written consent is documented. We expect the need for verbal consent prior to written consent to be rare; priority will be to consent right following a clinic visit. If recruitment cannot be completed in person, priority will go to contacting the patient over the phone, using the phone script. During the consenting process, if the patient indicates they do not want to participate in all aspects of the study, they can mark this on the consent form. Patients that fail to consent to the study will be asked to fill out a consent failure form to understand the reasons behind declining the study. This form will not collect any identifying information and will only record age, gender, race and ethnicity, and main reason for not wanting to consent to the study. We will keep these files in a secure database indefinitely.

Each patient’s oncologist will also participate in the study to provide their assessment of the patient’s preferences for involvement in treatment decision making, and their estimates of the patient’s chances of cure and survival. The oncologists are likely to provide estimates for several of the research participants. For their first assessment, they will be provided with a written explanation of the study. This will be considered their consent document, and by providing information on the assessment, they are consenting to participate in the study. We will not require the physician to provide written consent.

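### The kappa and chi-squared analyses in 11.2(3) make no allowance for patients who share an oncologist or for death without HCT, and the marginal Cox sentence supplies neither

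*Combined protocol and SAP*

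**What the plan says.** Section 7.0 brings the treating physician into the study: "Each patient’s oncologist will also participate in the study to provide their assessment of the patient’s preferences for involvement in treatment decision making". It adds that "The oncologists are likely to provide estimates for several of the research participants".

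Section 11.2(1) sets the scale: "we anticipate total sample of 1000 patients contributing to this analysis". Section 11.2(3) then lists four things:

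- The distribution of preferred involvement is compared "among patients who received HCT versus conventional therapy, using chi-squared test".
- A second set of chi-squared tests looks at how often a given answer is ranked highest.
- For patient-physician agreement, the plan says: "The weighted Kappa-statistic will be used to assess the level of agreement or disagreement". No standard error, interval or test is stated for it.
- As the one provision for correlation, the section says: "Marginal Cox model will be used to account for potential correlation between physician and patient preferences". It cites reference 108, whose title describes regression for multivariate failure-time data.

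Section 11.2(5) fits Cox models with HCT as the event and death without HCT as a competing risk. Institution enters as a covariate only in the outcome models of 11.3(2)(i). Sections 8.1.6 and 8.1.7 schedule the surveys at enrollment and at about 1, 3 and 6 months, the last only for patients without HCT. Section 11.2(3) does not say which of these is analysed.

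**The concern.** There are two separate problems.

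**Shared oncologists.** Kappa compares each patient's answer with a rating by an oncologist who also rates other patients. If oncologists differ in rating habits or in how well they read patients, the pairs are not independent, and an interval that treats them as independent can be too narrow. The plan recognises a correlation, but the tool it names is a failure-time method aimed at correlation between patient and physician preferences. The answers are not failure times.

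**Death without HCT.** The chi-squared tests split patients by whether they received HCT. A patient who dies without HCT falls in the conventional therapy column whether or not HCT was ever in prospect. If an answer goes with higher mortality, for instance because frailer patients prefer a different role in decisions, the table can show an association with HCT receipt when there is none with the rate of going to HCT.

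At stake is how preferences are reported as a reason for not having HCT. This bears on objective 5.1.1.2, the comparison of patients who did and did not proceed.

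**Working it through.** Section 11.2(3) gives no sample size, interval or power, so there is no figure to reproduce. The number of oncologists, the patients per oncologist and the intraclass correlation (ICC) are not in the documents; all values used for them below are assumptions.

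**1. Kappa.** Simulation with 1000 patients (11.2(1)), 20, 40 or 100 oncologists (50, 25 or 10 patients each), a true weighted kappa near 0.45 and an independent-pairs standard error (SE) near 0.0257.

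| Oncologist rating-habit share of variance | True SE / naive SE | Coverage of nominal 95% interval |
|---|---|---|
| 0.05 to 0.10 | 0.96 to 1.13 | 0.916 to 0.962 |
| 0.20 | 1.05 to 1.32 | 0.86 to 0.95 |
| 0.40 | 1.13 to 1.87 | 0.70 to 0.92 |

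If oncologists instead differ in accuracy (assumed SD 0.1 to 0.2, 20 to 100 oncologists), simulated coverage was 0.71 to 0.94. A hand check, taking a change in accuracy to move kappa one for one:

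- Formula: true SE ≈ √(0.0257² + SD²/K), with K oncologists.
- SD 0.1, K = 100: √(0.00066 + 0.00010) = 0.0276; ratio 1.07; coverage 2Φ(1.96/1.07) − 1 ≈ 0.93.
- SD 0.2, K = 20: √(0.00066 + 0.00200) = 0.0516; ratio 2.01; coverage 2Φ(1.96/2.01) − 1 ≈ 0.67.

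The simulated and approximate ranges agree roughly.

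**2. Chi-squared tests, clustering only.** These use patients' own answers, and HCT and non-HCT patients can share an oncologist. The approximate design effect is therefore 1 + (m − 1) × ICC(preference) × ICC(HCT), where m is the number of patients per oncologist. With m = 25 and both ICCs 0.10 it is 1 + 24 × 0.01 = 1.24. If either ICC is zero it is 1. Simulated size of the nominal 0.05 test, with five answer levels and 25% HCT:

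- only one of the two clusters: 0.040 to 0.060;
- both cluster modestly: 0.046 to 0.064;
- both ICCs 0.20: 0.063 to 0.121.

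**3. Chi-squared tests, death without HCT.** Section 11.1 assumes 25% HCT incidence at 2 years and 25% death without HCT.

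- Count: 0.25 × 670 = 167.5, about 168. Against the 505 not transplanted in 11.1, 168/505 = 33%. On the 1000 patients of 11.2(1), 0.25 × 1000 = 250.
- Mechanism, assuming constant hazards: equal risks of 25% and 25% over 2 years give each event a hazard of h = −ln(0.5)/4 = 0.173 per year. If an answer multiplies only the death hazard by r, the 2-year HCT proportion is [1/(1 + r)] × [1 − exp(−2h(1 + r))].
- r = 1: 25.0%. r = 1.5: 0.400 × (1 − 0.420) = 23.2%. r = 2.5: 0.286 × (1 − 0.297) = 20.1%.

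The HCT hazard is identical in all three, yet the proportions compared by the chi-squared test differ. In simulation with hazard ratios of 1.5 to 2.5 for death only, the test rejected in 8% to 24% of runs at a nominal 5%. The exact figure varies with how common the answer is and with the sample size.

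**4. The marginal Cox sentence.** Read generously, it could mean a Cox model for time to HCT with robust variance by oncologist. The text does not say so, and such a model would still leave kappa and the chi-squared tests as they are.

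**The case against.** The strongest reply is that 11.2(3) is supportive description. It states no kappa interval, so nothing wrong has been specified. The inference for objective 5.1.1.2 lies in 11.2(5), which already treats death without HCT as a competing risk over the candidate predictors. A Cox model with cluster-robust variance is itself a marginal Cox model, so the plan may lack only the event and the cluster unit.

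Much of this stands. For kappa, the fault is an unstated variance method, not a stated wrong one, and the 11.2(5) model is the right base for the fix. What does not stand is that nothing needs to change. The chi-squared tests are stated methods for comparing preferences by treatment received and do not carry over the competing-risk treatment, and no reading of the Cox sentence gives kappa a valid interval.

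Three stronger readings are tempting, and the documents do not support them:

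- A reader might apply 1 + (m − 1) × ICC to every analysis. With 5 to 20 patients per oncologist and ICC 0.05 to 0.10, it gives design effects of 1.2 to 2.9 and a true error of 7% to 25%. That formula suits a quantity clustered as a whole, not a comparison of patients' own answers between groups that share oncologists.
- A reader might infer that HCT decisions cluster by oncologist. Section 7.0 speaks only of oncologists' assessments and estimates.
- A reader might call all 168 deaths early. The 25% is death without HCT over 2 years and includes late deaths and deaths after HCT was declined.

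**Conclusion.** The point holds in limited form. As written, 11.2(3) has no method for shared oncologists, and the marginal Cox sentence does not provide one.

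For kappa, independent-pairs intervals may be too narrow. The effect is small if oncologists differ modestly in rating habit and material if they differ in accuracy or if habit effects are large. Which case applies cannot be settled from the documents. For the chi-squared tests, clustering is a minor matter unless both preference and HCT receipt cluster strongly.

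The larger issue for the chi-squared tests is that deaths without HCT, about a third of the non-HCT group on the plan's own assumption, are counted as conventional therapy. The 8% to 24% rejection rate is conditional on an assumed link between preference and mortality; without that link the problem does not arise.

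The HCT-rate estimates and the outcome models in 11.3 do not depend on these tests. The change is worth making because it is cheap and concerns how reasons for not having HCT are reported.

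**What to change.** In 11.2(3):

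1. Name the survey time point for each analysis. Enrollment is the natural choice for comparisons by HCT, since the 6-month survey excludes patients already transplanted.
2. Report weighted kappa with a confidence interval from a bootstrap that resamples oncologists with all their patients. Report the number of oncologists and the patients per oncologist.
3. Replace the marginal Cox sentence: base inference on preference variables on the 11.2(5) Cox model, with robust variance clustered on oncologist. State that the model is cause-specific, with follow-up for HCT ending at death. A subdistribution model, as used in 11.3, would carry mortality back into the HCT comparison.
4. Keep the chi-squared tables as description without P values, and show deaths without HCT as a separate column.
5. If the rule in 11.3 that all P values come from likelihood ratio statistics is meant to reach 11.2, make an exception, because clustered variance calls for Wald or robust score tests.

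The cost is SAP wording and possibly wider intervals. The surveys, deaths and HCT dates are already collected, and each physician survey is tied to a patient, so the oncologist identifier should be at hand.
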